Principal investigator: [name] Protocol Title: Autologous Regeneration of Tissue (ART) for Wound Healing IRB Study Number: 20180154 Version 3, Date: 02 Sep 2021 NCT: NCT03796988

Document Date/Effective Date: 10/11/2021

1) **Protocol Title**

Autologous Regeneration of Tissue (ART) for Wound Healing

2) IRB Review History*

N/A

3) **Objectives***

The study objectives include

- Assessment of pain on harvesting of skin donor sites (using a Visual Analog Scale)
- 2) Assessment of patient and physician tolerability (using a global assessment tool)
- 3) Time to healing of donor sites
- 4) Assessment of short term (2 months) quality of healing of donor site (using a scar assessment tool)

Secondary endpoints will be evaluation of wound healing of the recipient sites and histologic evaluation of the donor site.

4) Background*

Skin wounds sometimes are difficult to heal by primary closure and often require tissue substitution by autologous grafting requiring harvesting of donor skin [1, 2]. The latter may cause morbidities such as risk of infection, discoloration, pain, and scarring of both donor and recipient areas [3].

Full-thickness skin grafts (FTSG) are created when the entire dermis and epidermis are harvested. These grafts are typically used for acute full-thickness wounds where the wound can sustain and nourish the graft and improved cosmesis is important [4]. Split-thickness skin grafting (STSG) has been used to close large skin wounds, [5] and it involves the harvesting of the epidermis and upper dermis from a donor site. It is generally the preferred grafting method for restoring the structural integrity of chronic wounds, as the wound bed may not have the ability to support a FTSG [4]. Nevertheless, because deep dermal structures such sweat glands and hair follicles are not harvested, the STSG is functionally abnormal. Before the grafting process takes place, STSGs are commonly meshed and enlarged, increasing the coverage area and allowing fluid drainage. However, the meshing process produces a "fish-net" appearance of the grafted skin [1]. Other limitations include healing of the donor site, which often is delayed and leaves unappealing pigmentary changes and, at times, scar formation [4].

Currently, engineered "off the shelf" grafts such as cadaveric skin, xenografts, and artificial skin substitutes are being used in the management of chronic, difficult to heal wounds. Skin substitutes work by providing cells, growth factors, and other key elements that promote healing while preventing extracellular matrix degradation [6]. However, these only offer transient wound coverage, and require secondary healing of the wound itself. Thus, autologous skin grafting continues to

be necessary. Scar formation at the donor and grafted site remain most troublesome morbidities in autologous skin grafting. Scar tissue is stiff, dysfunctional, often painful, and tends to contract over time, producing skin irregularities [7].

In contrast, skin remodeling is a process that substitutes missing tissue while preserving tissue architecture. While scarring is triggered by large-scale tissue damage, remodeling is stimulated by microscopic tissue damage [8]. This principle became clear when fractional photothermolysis (FP) was developed that is currently used for photoaged skin treatment and wound scars [8, 9]. In FP, laser microbeams are used to produce microscopic thermal injury per cm2 of skin surface, which causes very thin columns of tissue damage or ablation. It has been found that columns less than 500 μ m in diameter heal promptly without scarring [1, 10]. FP involves full-thickness (i.e. complete epidermis and dermis) tissue injury in which the epidermis closes within 1 day, and the dermal damage is fixed in around 2 weeks, followed by tissue remodeling without scarring [9].

Because the experience with FP showed that millions of small, full-thickness columns of skin tissue can be removed without scarring, it was hypothesized that full-thickness microscopic skin tissue columns (MSTCs) could be harvested from healthy skin with insignificant donor site-morbidity and that these MSTCs could function as a graft to accelerate wound healing.

To explore this, a prototype device was developed that can harvest hundreds of fullthickness columns of skin tissue (500 micrometer diameter) using single-needle, fluid-assisted harvesting technology. The harvested MSTCs can subsequently be placed directly onto a wound to aid in healing.

With conventional full thickness grafts and split thickness grafts, the donor area requires sometimes a period of immobility, requiring attentive wound care and pain management [11]. The ART may provide a more effective method of harvesting skin with minimal or no pain, healing rapidly with little scarring [1]. This can take place in an outpatient setting, with the use of only local anesthesia.

5) Inclusion and Exclusion Criteria*

Inclusion criteria:

- Adults from 18 to 90 years of age.
- Patients that have a chronic wound in any area of the body defined as having been present for at least 30 days of duration.
- Able and willing to give consent for the study.

Exclusion criteria:

- Pregnant women (Urine hCG test will be performed at baseline on women of child bearing potential).
- Adults unable to consent.
- Prisoners.
- Subjects requiring concurrent systemic antimicrobials during the study period for any infection.
- Subjects with leg lesions and clinically significant and unreconstructed peripheral arterial disease.
- Subjects who are receiving immunosuppressive agents, radiation therapy, or cytotoxic agents.
- Subjects who require treatment for a primary or metastatic malignancy (other than squamous or basal cell carcinoma of the skin).
- Subjects with other conditions considered by the investigator to be reasons for disqualification that may jeopardize subject safety or interfere with the objectives of the trial (e.g., acute illness or exacerbation of chronic illness, lack of motivation, history of poor compliance).

6) Number of Subjects*

The University of Miami Wound Care Center ([name]) will enroll 30 subjects locally.

7) Study-Wide Recruitment Methods*

Subject recruitment will be from physician referrals from the University of Miami Wound Care Center and Stanford University Advanced Wound Care Center.

8) Study Timelines*

This study will take 1 year to complete. The first 9 months will be dedicated to subject enrollment and follow up. The last 3 months will be dedicated for data analysis and dissemination.

9) Study Endpoints*

The study objectives include:

- Assessment of pain on harvesting of skin donor sites (using a Visual Analog Scale)
- 2) Assessment of patient and physician tolerability (using a global assessment tool)
- 3) Time to healing of donor sites.
- 4) Assessment of short term (2 months) quality of healing of donor site (using a scar assessment tool)

Secondary endpoints will be evaluation of wound healing of the recipient sites and histologic evaluation of the donor site.

10) **Procedures Involved***

Eligible wounds are to be present for at least 4 weeks to be considered chronic. The patient will also have to have an area of intact skin that can serve as the skin donor area for the wound.

Once patients are determined to be eligible to participate, they will sign consent, and then the wound and the donor area will be photographed. The patients will have their wound assessed clinically and through photography.

The donor area will be anesthetized with injected local anesthesia, harvested with the ART device, and bandaged with an occlusive dressing. The skin harvested will be placed on the recipient wound area. The area will be bandaged will a non-stick silicone dressing (covered by appropriate primary and secondary dressings) and left intact for 1-7 days.

The patient will leave the bandage at the recipient site and donor area untouched until they are seen again at the follow up visits.

At each weekly visit, the donor site will be assessed for pain and itch with a Visual analogue scale (VAS), for scar formation, and for cosmetic appearance. The recipient area will be assessed for healing percentage, pain and itch VAS.

At visit 6, day 56 and approximately 2 months after the baseline, an optional 3mm punch biopsy will be collected at the donor site. The biopsy will be formalin fixed and paraffin embedded in order to undergo histologic evaluation by H&E and elastic tissue stains. Patient satisfaction will be determined at the end of the study.

Follow up visits will take place in: Visit #2 Day 7: 7 ± 1 days later Visit #3 Day 14: 7 ± 1 days later Visit #4 Day 21: 7 ± 1 days later Visit #5 Day 28: 7 ± 1 days later Visit #6 Day 56: 30 ± 4 days later

11) Data Management*

All of the data, including records of subjects, source documents, and inform consent will be kept in the study centers under lock for 6 years after the study finished. After 1 year of study closure, documents will be sent to off-site storage (Iron Mountain).

12) Provisions to Monitor the Data to Ensure the Safety of Subjects*

The study team will be responsible for protecting the safety, rights, and well-being of study participants.

Recording and reporting of adverse events that occur during the course of the study will help to ensure the continuing safety of participants. Local and systemic adverse

> events will be monitored during the study. In case an adverse event does take place, a documentation system will be used to record the following information: description of event, time/date of onset, duration of reaction, does/frequency/route of drug administration, reversibility or sequelae, therapy (if any), and seriousness/severity (based on Common Terminology Criteria for Adverse Events v4). If a subject experiences an adverse event assessed at a Grade 3 according to CTCAE v4, the subject will not receive additional testing and will be followed until the adverse event resolves or stabilizes.

Study stoppage will occur if 15 subjects complete the study (at each site) or if a severe adverse event occurs.

The PI will be responsible for monitoring ongoing activates to ensure compliance with regulatory and protocol requirements, data quality, and participant safety.

13) Withdrawal of Subjects*

All subjects are free to withdraw from participation in this study at any time, for any reason, and without prejudice.

Subjects must be withdrawn from the study if:

- 1) A subject withdraws consent.
- 2) The Investigator believes it is in the best interest of the subject to be removed from the study.

The data collected before the withdrawal will still be used in data analysis.

14) Risks to Subjects*

1. Protected Health Information (PHI) will be collected during the study. Every attempt will be made to ensure that this PHI is kept secure. All study data will be kept in a locked office and kept under password protection on a computer that is only accessible by study personnel.

2. There are mild or moderate risks associated with performing a skin biopsy: a risk for a local infection and/or a small scar, and the possibility that at the biopsy site a raised scar could form, e.g. keloid (this depends on individual propensity for scar formation).

3. There are mild or moderate risks associated with ART system: a risk for a local infection and/or a small scar, and the possibility that a raised scar could form, e.g. keloid (this depends on individual propensity for scar formation).

15) Potential Benefits to Subjects*

There may be the benefit of the target wound to be treated and healed with the use of this new technology as well as with use of standard of care therapy in the case of venous leg ulcers.

16) Vulnerable Populations*

No pregnant women, children, prisoners, or cognitively impaired adults will be enrolled in this study.

17) Multi-Site Research*

The second site for this study is Stanford University Advanced Wound Care Center (AWCC; [name]). The PI of that site will conduct this study under their institution's IRB oversight.

[name], the PI of the UM site will not be overseeing the Stanford site.

De-identified data will be shared between sites for data analysis.

18) Sharing of Results with Subjects*

Results of this study will not be shared with the subjects, unless through scientific publication.

19) Setting

Potential subjects will be identified and recruited from department physicians and study team members from the UMH Dermatology outpatient clinic ([name]) and the UMH Wound Care Center ([name]).

Research procedures will be performed in the Dermatology Research Clinic ([name]).

20) **Resources Available**

[name], MD, the Principal Investigator is an Assistant Professor in the Department of Dermatology. He has extensive training performing clinical trials focusing on wounds. He will oversee the clinical portion of this project, including enrollment of and care of patients.

All study personnel will complete their CITI training and be adequately informed about the protocol and study procedures. All duties and functions are appointed and overseen by the PI.

21) Prior Approvals

N/A

22) **Recruitment Methods**

Potential subjects will be identified and recruited from department physicians and study team members from the UMH Dermatology outpatient clinic ([name]) and the UMH Wound Care Center ([name]).

Subjects will be compensated \$25 per study visit.

23) Local Number of Subjects

Thirty total subjects will be enrolled in this study.

24) Confidentiality

Every attempt will be made to ensure any information gathered is kept secure. All study data will be kept in a locked office within the Dermatology Research Clinic ([name]) and kept under password protection on a computer that is only accessible by study personnel.

Data that is de-identified will be shared between sites for data analysis.

25) Provisions to Protect the Privacy Interests of Subjects

Study subjects will only be asked to provide personal information to approved study personnel, who will ensure the subject is at ease with the situation. Study personnel will clearly explain that the subject does not have to answer any questions or provide any sample they are uncomfortable about.

Medical records will be accessed to review wound history after the subject gives written study ICF and HIPAA consent.

26) Compensation for Research-Related Injury

Treatment will be available if enrolled subjects get sick or injured. However, the subject or the subject's insurance will be responsible for these costs. Funds to compensate for pain, expenses, lost wages, and other damages caused by injury are not available.

27) Economic Burden to Subjects

There will be no charges to the subjects that agree in participating in this study.

28) Consent Process

The research team will follow the "HRP-090 SOP: Informed Consent Process for Research" to obtain informed consent and the "HRP-091 SOP: Written Documentation of Informed Consent" to document informed consent in writing.

Study personnel will meet with each potential subject to discuss the study in detail, answer questions, and allow the subject to read the entire consent form. The informed consent form explicitly states the rationale for the study and requirements for participation, both before and during the session. The informed consent form states that subjects may discontinue participation or be terminated from the study at any time.

> All pertinent aspects of the study will be explained to the subject before he or she signs the informed consent form. A signed informed consent form will be obtained from the subject before any activity or treatment is undertaken as part of the study.

Non-English Speaking Subjects

ICFs and subject surveys will be translated into Spanish.

29) Process to Document Consent in Writing

The research team will follow the "HRP--091 SOP: Written Documentation of Informed Consent" to document informed consent in writing.

30) Drugs or Devices

The ART system device and cartridges will be securely stored in the UMH Dermatology Research Clinic. Only approved and designated study personnel will have access to the system. Only approved, designated, and trained study personnel will administer the device.

The ART system from Medline Industries, Inc. is a medical device already on the market within the US.

31) Study Milestones

Study milestones are the completion of visits by enrolled subjects.

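### The optional donor-site biopsy is taken at the last scheduled visit, so the complications the protocol names for it have no planned ascertainment and are likely to be under-reported

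*Protocol*

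**What the plan says.** Section 10 (Procedures Involved) fixes the biopsy to the final visit: "At visit 6, day 56 and approximately 2 months after the baseline, an optional 3mm punch biopsy will be collected at the donor site". The follow-up list in the same section ends with "Visit #6 Day 56: 30 ± 4 days later".

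Section 14 (Risks to Subjects) describes the risks of the procedure: "There are mild or moderate risks associated with performing a skin biopsy: a risk for a local infection and/or a small scar". It adds "the possibility that at the biopsy site a raised scar could form, e.g. keloid". The next item in that section gives the same risks for the ART system.

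Section 12 (safety monitoring) relies on "Recording and reporting of adverse events that occur during the course of the study" and says that local and systemic "events will be monitored during the study". It gives no date on which collection ends for an individual subject. For an event assessed at Grade 3, the subject "will be followed until the adverse event resolves or stabilizes". No such statement is made for lower grades.

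Section 10 also says "Patient satisfaction will be determined at the end of the study".

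**The concern.** An infection or a raised scar takes time to appear after the wound is made. When the wound is made at the last planned contact, the protocol provides no occasion on which anyone asks about these events or looks for them. The biopsy serves a secondary histology endpoint, and Section 15 names no benefit from it to the subject. It is therefore a research procedure whose disclosed risks should be recorded with some care.

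What is at stake is how a safety statement may be read. If the report says that few or no biopsy complications were recorded, the reader cannot tell whether they did not occur or were not sought. The four main objectives and the follow-up of the harvest itself to Day 56 are not at issue.

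**Working it through.** The plan states no figure for this point, and no power or sample-size calculation applies. The check compares the schedule with the named risks and the adverse-event provisions.

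**Inputs**
- Biopsy: Visit 6, Day 56, optional (Section 10).
- Last scheduled contact: Visit 6, Day 56 (Section 10). Section 31 defines study milestones as completed visits, and none remains after Visit 6.
- Follow-up visits after the harvest: Visits 2 to 6, on Days 7, 14, 21, 28 and 56 (Section 10).
- Named risks: the same three for the biopsy and the harvest (Section 14).

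**Step 1. Scheduled follow-up after each procedure** = day of last scheduled visit minus day of procedure.

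| Procedure | Named risks | Scheduled follow-up | Later visits |
|---|---|---|---|
| ART harvest (baseline) | infection, small scar, raised scar or keloid | 56 − 0 = 56 days | 5 |
| Punch biopsy (Visit 6) | infection, small scar, raised scar or keloid | 56 − 56 = 0 days | 0 |

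**Step 2. Does the visit window change this?** If the stated intervals are chained, Visit 6 falls nominally on Day 4 × 7 + 30 = 58. The earliest day is 4 × 6 + 26 = 50 and the latest is 4 × 8 + 34 = 66. The biopsy is tied to the visit itself, so the follow-up after it is 0 days wherever Visit 6 falls.

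**Step 3. Do the general safety provisions fill the gap?**
- Recording during the study allows a late event to be entered if it becomes known. It does not create an occasion to learn of it.
- Follow-up to resolution or stabilization is stated only for Grade 3, while Section 14 calls the biopsy risks mild or moderate. An event must in any case be detected before that rule can apply.

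**Step 4. How many subjects?** Only those who accept the biopsy. Uptake is not given, so the range is 0 to 30 on the total in Section 23. Section 6 gives 30 for the Miami site alone. If subjects at the second site came on top of these, the ceiling would be higher.

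**The case against.** The strongest reply is that zero scheduled visits is not zero observation, and much of it stands. A reader might infer that biopsy complications cannot appear in the safety data at all, or that the trial would report none whatever happened. The documents do not support that:
- Section 12 sets no per-subject cut-off at Visit 6.
- Section 8 gives nine months to enrolment and follow-up, so early subjects finish while the study is still running.
- Section 19 recruits from the institution's own dermatology clinic and wound center, and Section 26 says treatment for injury will be available, though at the cost of the subject or the insurer.
- An immediate reaction at Visit 6 could be recorded there.
- The consent pages are not shown, so one cannot conclude that subjects have no instruction on whom to contact.

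It is also fair to say that Section 12 asks for duration, sequelae and therapy for any adverse event. A lower-grade event, once reported, would presumably be followed far enough to complete those fields. These routes still depend on the subject coming forward.

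A second reply is that the timing is defensible: taking the biopsy last keeps a punch wound out of the earlier donor-site assessments and aligns histology with the 2-month scar rating. This is accepted, and the point does not call for moving the biopsy.

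A reader might also infer that the Visit 6 scar and satisfaction ratings are distorted by a fresh wound at the donor site. That would follow only if the biopsy came first. The protocol does not state the order, and nothing in it implies that one. This is a matter for clarification, not a shown bias.

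**Conclusion.** The concern holds in this form: the infection, scar and keloid risks named for the optional biopsy have no scheduled ascertainment, against five visits for the same risks after the harvest. They can be recorded if volunteered, but under-reporting is likely. The degree of under-reporting cannot be computed, because the documents give neither an event rate nor the biopsy uptake.

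The conclusion assumes that the visit list in Section 10 is complete and that no post-biopsy contact is set out in material not shown. It concerns the safety record of biopsied subjects only and leaves the main endpoints intact. It is a cheap improvement worth making, not a defect that undermines the trial.

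**What to change.** 1. In Section 10, add one remote adverse-event contact after the biopsy for subjects who accept it, with the timing set by the investigator.
2. In Section 12, state that adverse-event collection for these subjects runs to that contact.
3. One call may be too early to detect a keloid. The report should therefore say that late scarring at the biopsy site was not systematically assessed.
4. As a minor clarification, state in Section 10 that the Visit 6 donor-site ratings, satisfaction rating and photographs are completed before the biopsy.

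The cost is one call per biopsied subject by existing staff and a short amendment. Item 4 costs nothing beyond the sentence.

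### Do the two-day mismatches in the Visit 6 date and in the chronic-wound definition call for a change to the plan?

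*Protocol*

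**What the plan says.** Section 10 of the protocol (Procedures Involved) lists five follow-up visits, each with a day label and an interval. The weekly visits follow one pattern, for example "Visit #3 Day 14: 7 ± 1 days later" and "Visit #5 Day 28: 7 ± 1 days later". The last entry is "Visit #6 Day 56: 30 ± 4 days later". The text above the list gives the optional donor-site biopsy the same label: "At visit 6, day 56 and approximately 2 months after the baseline". Section 9 (Study Endpoints) includes an objective set at about that time: "Assessment of short term (2 months) quality of healing of donor site (using a scar assessment tool".

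On entry, the inclusion list in Section 5 requires a chronic wound, "defined as having been present for at least 30 days of duration". Section 10 opens with "Eligible wounds are to be present for at least 4 weeks to be considered chronic".

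Section 17 (Multi-Site Research) adds that "the PI of the UM site will not be overseeing the Stanford site".

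**The concern.** Two pairs of statements disagree on their face.

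First, label and interval agree for Visits 2 to 5 but not for Visit 6, so that visit seems to have two target days. The list also does not say whether an interval starts from the scheduled or the actual date of the previous visit. A visit could then be in window on one reading and a deviation on another. Visit 6 is the only scheduled visit near 2 months, so it is the natural occasion for the 2-month donor-site scar assessment, and it also carries the optional biopsy for the histology endpoint.

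Second, a wound of 28 or 29 days fails the Section 5 definition yet meets the Section 10 description of a chronic wound. The investigator at the first site does not oversee the second, so the two sites might settle such a case differently.

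If either mismatch were large, the 2-month scar data would be taken at inconsistent times, or the sites would enrol different populations.

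**Working it through.** **Inputs (protocol Sections 5 and 10).** Labels for Visits 2 to 6: Days 7, 14, 21, 28, 56. Intervals: 7 days (tolerance 1) four times, then 30 days (tolerance 4). Entry thresholds: 30 days (Section 5) and 4 weeks (Section 10).

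**Visits 2 to 5.** Adding each interval to the previous visit gives 0 + 7 = 7, 7 + 7 = 14, 14 + 7 = 21 and 21 + 7 = 28. All four labels are reproduced. This works only if intervals run from the previous visit, so the labels imply that much of the anchor.

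**Visit 6.** The same rule gives 28 + 30 = Day 58, against the label Day 56. The gap between labels is 56 − 28 = 28 days, against a stated 30. The difference is 2 days. Counting from baseline would give Day 30, which cannot be meant.

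**Can label and interval both be met?** The interval allows 30 − 4 = 26 to 30 + 4 = 34 days after Visit 5. With Visit 5 on Day 28, Day 56 is 28 days later and lies inside that range.

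**Effect of the anchor on Visit 6.**

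| Reading | Calculation | Visit 6 range |
|---|---|---|
| From scheduled Day 28 | 28 + 26 to 28 + 34 | Days 54–62 |
| From actual previous visits | Visit 5: 4 × 6 = 24 to 4 × 8 = 32; Visit 6: 24 + 26 to 32 + 34 | Days 50–66 across subjects |
| Tolerance applied to the label | 56 − 4 to 56 + 4 | Days 52–60 |

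The third reading has the weakest support, because the tolerance is attached to the 30-day interval and not to the label. In the second row, Days 50–66 is an envelope over subjects; each subject's own window spans 34 − 26 = 8 days from end to end.

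**Where Day 56 falls outside.** If Visit 5 took place on day d, the window is d + 26 to d + 34. Day 56 is inside when d lies between 56 − 34 = 22 and 56 − 26 = 30. Visit 5 can fall on Days 24 to 32, so Day 56 is outside only for d = 31 (window 57–65) or d = 32 (window 58–66). With whole-day deviations, d = 31 needs three of the four weekly visits a day late and none early, and d = 32 needs all four late. Day 58 is inside when d lies between 58 − 34 = 24 and 58 − 26 = 32, which covers every permitted Visit 5.

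**Entry.** 4 × 7 = 28 days. Wounds of 28 or 29 days meet the Section 10 statement and fail the Section 5 one. Wounds of 30 days or more meet both, and wounds under 28 days meet neither.

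**The case for a change.** The strongest case for acting is that eligibility and visit timing are instructions to sites, so an analysis plan cannot repair them afterwards. An analysis plan can set analysis windows, but it cannot tell a site whom to enrol or when a visit counts as a deviation. The protocol states no order of precedence between Sections 5 and 10. The sites work under separate oversight and share data for analysis. A clarification would cost only wording. In addition, if intervals run from actual visits, a subject seen for Visit 5 on Day 31 or 32 would be out of window on the labelled day.

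Much of this stands as description. The inconsistencies are genuine, they are in the current text, and no reading makes the Visit 6 line internally exact. The out-of-window case is also real, although it needs nearly every weekly visit to run late.

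What does not stand is the step to consequences. The anchor is partly given, since only counting from the previous visit reproduces the earlier labels. The Section 10 sentence on wound age sets a minimum for calling a wound chronic; it does not say that meeting it is enough for enrolment, and the formal inclusion list still applies. A site that respects both statements has a workable rule. That the sites would in fact diverge is conjecture: Section 17 says who oversees whom, not that the sites read the criteria differently.

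**Conclusion.** The mismatches are correctly identified: 2 days in the Visit 6 target (Day 56 against Day 58) and a 2-day band of wound age (28 and 29 days). They are clerical. In each pair both statements can be followed at once, at least on the nominal schedule, and the protocol ties no exclusion, analysis set or other consequence to a visit on an edge day. Even the widest reading, Days 50 to 66, stays within 8 days of Day 58, for a time point that the protocol itself calls approximate.

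Whether intervals start from scheduled or actual dates is a detail that sites and analysts settle in practice, and actual visit dates can be used wherever timing matters. Bringing the label, the interval and the two wound-age statements into line would be tidying, with the values for the sponsor and investigator to choose. It would not change what the trial does or what it can conclude.

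This rests on three assumptions: that actual visit dates are recorded, that donor-site scar quality does not change materially over a few days around 2 months, and that few if any candidates have a wound exactly 28 or 29 days old. The protocol gives no figures to test the last two.
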